7.10.3.2 Contraception

Subjects undergoing OIT are at increased risk for experiencing allergic reactions and may be at increased risk for experiencing anaphylaxis. Anaphylaxis can cause a dangerous drop in BP; and if this were to occur during pregnancy, it could result in compromised placental perfusion and significant risk to the fetus.

Pregnancy is a time when the mother's immune system undergoes complex and incompletely understood changes that are believed to reduce the risk of a maternal immune reaction directed against the fetus. It is also a time when the fetus's immune system is developing. OIT, at its core, entails repeated stimulation of the immune system to affect changes in its makeup and function. What effects OIT-induced changes in the immune system might have on the course of pregnancy or fetal development are currently unknown. Accordingly, female subjects of childbearing potential are required to practice approved and effective birth control for the duration of the current study.

Study personnel are requested to address questions of sexual history and counselling in relation to contraception using sensitivity and a patient-centered approach and, if possible, to hold discussions regarding sexual history and contraception with adolescent female subjects in a private setting.

Female subjects are to use a highly effective single method of birth control, defined as one that results in a low failure rate (ie, less than 1 percent per year) when used consistently and correctly. Acceptable methods of birth control are the following:

- Combined (oestrogen and progestogen containing) hormonal contraception associated with inhibition of ovulation (oral, intravaginal or transdermal)
- Progestogen-only hormonal contraception associated with inhibition of ovulation (oral, injectable or implantable)
- Intrauterine device (IUD)
- Intrauterine hormone-releasing system (IUS)
- Bilateral tubal occlusion
- Sexual abstinence

7.11 Stopping Rules

7.11.1 Overall Stopping Rules

The study will be suspended at any time if a treatment-associated death occurs in a subject on active therapy, or if the second of 2 subjects is admitted to the hospital, within 6 months of the first, as a direct consequence of dosing with IP. Suspension of the study will entail halting the enrollment of subjects and refraining from any dose increases, but will not entail cessation of dosing unless so directed by the relevant regulatory agency(ies), or advised by the DSMC and agreed to by the sponsor. The suspension will not be lifted and dose escalation will not be resumed until the information has been discussed with regulatory authorities and the regulatory authorities either concur with resumption of up-dosing or direct discontinuation of the study in their jurisdictions.

The DSMC will also be periodically reviewing safety data, and can also recommend, in its judgment, halting the study for any substantial imbalance in AEs, apart from anticipated allergic dosing symptoms.

Aimmune additionally reserves the right to discontinue the study at any time for any reason. The regulatory health authority(ies) and IRBs/ECs will be notified in the event of study discontinuation.

In the event of early study closure, subjects who complete at least 9 months of study treatment and tolerate the 300 mg/d dose for at least 4 weeks may have the Exit DBPCFC and complete the study. AR101-treated subjects who tolerate a single highest challenge dose of at least 300 mg peanut protein (443 mg cumulative) in the Exit DBPCFC and placebo-treated subjects will be eligible to enroll in ARC008. In this situation, AR101-treated subjects who complete at least 9 months of study treatment and tolerate 300 mg/d for at least 4 weeks, but do not tolerate the single challenge dose of 300 mg peanut protein in the ARC010 Exit DBPCFC, may enroll in ARC008 if continued treatment is determined to be safe per investigator judgment and after discussion with the medical monitor. AR101-treated subjects who complete at least 9 months of study treatment but do not tolerate 300 mg/d for at least 4 weeks will not have the Exit DBPCFC but may be eligible to enroll in ARC008 if continued treatment is determined to be safe per investigator judgment and after discussion with the medical monitor.

7.11.2 Individual Stopping Rules

Individuals may stop the study at any time if they experience subjectively intolerable AEs or dosing symptoms. They must halt up-dosing and re-start with a reduced dose if more than 3 days of dosing are missed. Seven or more consecutive days of missed dosing due to non-compliance constitutes an individual stopping rule, as does a significant number of episodes of missed dosing (ie, 3 or more consecutive days on at least 3 occasions) during the Up-dosing Period. Missing 15 or more consecutive days of dosing for any reason also constitutes an individual stopping rule. [Section 4.3.1](#) provides additional individual stopping rules.

Occurrence of any of the following will result in the cessation of dosing:

- Failure to accomplish up-dosing of IP after 3 attempts
- Failure to identify a tolerated dose of IP after 3 attempts at dose reduction
- Administration of 3 or more doses of epinephrine for the treatment of any dose-related allergic reaction.

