4.3 Premature Subject Termination from the Study

4.3.1 Criteria

No subject randomized into this trial who discontinues treatment for any reason will be replaced.

Unless required for safety reasons (ie, medical treatment of an SAE), subjects eligible for an Exit DBPCFC will not be unblinded to their treatment assignment until after the subject completes the Exit DBPCFC and after all major data queries for the subject are resolved, and the follow-on study ARC008 is available at the study site. Subjects who are considered escalation failures will be unblinded once the trial database has been locked and treatment assignment unblinded.

Any subject will be prematurely terminated from additional study drug treatment and will be excluded from any further study procedures (with the exception of safety follow-up) for the following reasons:

1. Life-threatening symptoms (CoFAR Grade 4; refer to [Table A4](#) in [Appendix 4](#)), including, but not limited to, anaphylaxis resulting in hypotension, neurological compromise, or mechanical ventilation secondary to peanut OIT dosing or any peanut food challenge
2. Severe allergic hypersensitivity symptoms (CoFAR Grade 3; refer to [Appendix 4](#)) that require intensive therapy (to be determined by the investigator, but may include such interventions as intravenous (IV) epinephrine, intubation, or admission to an intensive care unit) or those that are recurrent. Subjects who experience severe symptoms (eg, severe nausea, rhinorrhea, or pruritus) that are not life-threatening, not requiring intensive therapy, and not associated with any other features indicating a serious clinical condition, and who the investigator feels are suitable to continue with the study, will be discussed with the medical monitor and may continue the trial under close supervision, if both the Investigator and the medical monitor deem it appropriately safe to do so
3. Pregnancy
4. Non-adherence (non-compliance) with study product dosing, as indicated by missing > 7 consecutive dosing days on any 1 occasion, or 3 consecutive dosing days on 3 or more occasions during the Up-dosing Period, as this could constitute a potential safety issue

5. Medically indicated circumstances (eg, as part of the treatment for intercurrent AEs) that require missed study product dosing for >14 consecutive days, except for the voluntary 30-day hiatus for AEs occurring at or before the 20-mg dose

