6.8 Missed Peanut OIT (IP) Doses During Up-dosing

Risk due to missed doses of study product is believed to be highest during the Up-dosing Period. The procedures to be followed after missed consecutive doses of study product during the Up-dosing Period is depicted in [Figure 5](#). Explanatory text follows the figure.

Figure 5: Procedures Following Missed Consecutive Doses of Peanut OIT

AE= AE; GI=gastrointestinal; CRC=clinical research unit; IP=investigational product

- Miss **1 dose** – The next dose would be at the current dose level and could be given at home.
- Miss **2 consecutive doses** – The next dose would be the current dose level and could be given at home.
- Miss **3 consecutive doses** – The next dose would be the current dose and would be given under supervision in the CRC.
- Miss **4 consecutive doses** – The next dose would be the current dose and would be given under supervision in the CRC.
- Miss **5 to 7 consecutive doses** – Initiate the next dose at approximately 50% of the last tolerated dose (to the nearest feasible available whole dose that is $\leq 50\%$ of the last tolerated dose). This dose is to be administered under supervision in the CRC. If tolerated, dose escalation may resume with dose increases of 1 dose level occurring no more frequently than weekly and generally no less frequently than every 4 weeks until the subject has returned to the dose level at which the lapse in dosing occurred. If symptoms occur, the dosing guidelines for the Up-dosing Period apply.
- Missing **> 7 consecutive days** of dosing due to non-compliance (ie, for any reason other than treatment of an AE or an IP dispensing error), constitutes an individual stopping rule and the subject is to stop taking IP. The subject will be asked to return to the CRC 14 to 16 days following their last dose of IP to undergo an Early Discontinuation Visit ([Section 6.4](#)).
- Additionally, excessive missed dosing, defined as **3 consecutive days of missed doses on 3 occasions during the Up-dosing Period or on 3 occasions during the Maintenance Period**, for any reason other than treatment of an AE or an IP dispensing error, constitutes an individual stopping rule and the subject is to stop taking IP. The subject will be asked to return to the CRC 14 to 16 days following their last dose of IP to undergo an Early Discontinuation Visit ([Section 6.4](#)).

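### Protocol sections 6.8 and 7.11.2 give incompatible restart instructions after exactly 4 consecutive missed doses in Up-dosing; the repeated-lapse stopping rule also differs in the periods it covers

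*Protocol*

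**What the plan says.** Three sections of the protocol give rules for missed doses.

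- **Section 6.8** is a graded list for the Up-dosing Period. For 4 consecutive missed doses it says "The next dose would be the current dose and would be given under supervision in the CRC", the same instruction as for 3. For 5 to 7 it says "Initiate the next dose at approximately 50% of the last tolerated dose". A gap of more than 7 days stops treatment if it occurred "for any reason other than treatment of an AE or an IP dispensing error), constitutes an individual stopping rule". The next bullet stops treatment after 3-day lapses "on 3 occasions during the Up-dosing Period or on 3 occasions during the Maintenance Period", with the same exemption for AE treatment and dispensing errors.
- **Section 7.11.2** is a short paragraph: "They must halt up-dosing and re-start with a reduced dose if more than 3 days of dosing are missed". It also makes repeated episodes a stopping rule, defined as "3 or more consecutive days on at least 3 occasions) during the Up-dosing Period".
- **Section 4.3.1, item 4**, under non-adherence, ends treatment for "3 consecutive dosing days on 3 or more occasions during the Up-dosing Period" as well as for a single gap of more than 7 days. Item 5 deals separately with medically indicated gaps.

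Section 9.2.1 counts anyone who discontinues OIT before the Exit DBPCFC as a treatment failure.

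**The concern.** The restart dose after a gap is a mandatory instruction, given to sites treating peanut-allergic children with peanut protein. Section 6.8 itself says the risk from missed doses is thought to be greatest during Up-dosing. For one gap length the protocol gives two restart instructions, so the dose a child receives depends on which section the site opens. Whichever section a site follows, it departs from the other, which also makes it unclear what counts as a deviation.

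The repeated-lapse rule matters for a different reason, because it stops treatment. A subject stopped in Maintenance under 6.8 has no Exit DBPCFC and is a failure in the primary analysis. A site that reads only 4.3.1 or 7.11.2 finds no such rule for Maintenance and could keep the subject in the trial.

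**Working it through.** The point rests on wording. The planning figures in section 9.4 are not in dispute: full enumeration of Fisher's exact test with 120 and 40 subjects gives 82.8% power at 39% versus 15% and 92.1% at 43% versus 15%, in line with the stated minimum of 80% and 90%.

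**Side by side**

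| Case | 6.8 | 7.11.2 | 4.3.1 | Result |
|---|---|---|---|---|
| 4 consecutive missed doses, Up-dosing | Current dose, supervised | Reduced dose, mandatory | Silent | Contradiction |
| Three 3-day lapses, non-compliance, Up-dosing | Stop | Stop | Stop | Agreement |
| Three 3-day lapses, non-compliance, Maintenance | Stop | Not listed | Not listed | Scope differs |
| Three 3-day lapses, AE treatment or dispensing error, Up-dosing | Exempt | Exemption not repeated | Framed as non-adherence; item 5 treats medical gaps separately | Editorial |

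**Where the restart conflict lies.** For gaps of up to 7 consecutive doses, 7.11.2 requires a reduction at 4, 5, 6 and 7, and 6.8 requires one at 5, 6 and 7. At 3, neither requires one. At 5 and 6 both do, although only 6.8 gives a size. The restart-dose conflict is therefore at exactly 4 consecutive doses. Section 7.11.2 does not say that the days must be consecutive. If they need not be, two separate 2-dose gaps (2 + 2 = 4 days) would also trigger a reduction there, while 6.8 resumes the current dose after each. (At exactly 7 days of non-compliance the sections differ on stopping; that is a separate matter.)

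**Size in dose.** Section 7.11.2 gives no size, so the least that it can mean on the Table 2 schedule is one level down.

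- From 240 mg: 240 to 200, and 40/240 = 17%.
- From 80 mg: 80 to 40, and 40/80 = 50%. The steps down from 6, 12 and 40 mg are also 50%.
- All other one-level steps in Table 2 fall between these values.

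**Does the 4-dose conflict reach the primary endpoint?** Not directly, since both instructions keep the subject on treatment. Indirectly, section 6.3.3.1 resets the 2-week schedule after a reduction, and a subject not at 300 mg/d by Week 40 gets no Exit DBPCFC. The uninterrupted schedule takes about 20 weeks, so the slack is 40 - 20 = 20 weeks. The reset costs at least 2 of those. One such event is unlikely to use up the slack.

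**Effect of a Maintenance stop on the response rate.** Per subject stopped under one reading and kept under the other:

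- If the subject would have responded: AR101 1/120 = 0.83 percentage points; placebo 1/40 = 2.5 points.
- If the subject would not have responded: 0 in either arm.
- Averaged at the planning rates of section 9.4, taken as an assumption: AR101 0.39/120 = 0.33 points; placebo 0.15/40 = 0.38 points.

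The AR101 average may be low, because a subject in Maintenance has already reached 300 mg/d while the 39% includes subjects who never do. The safe statement is the range: 0 to 0.83 points per AR101 subject and 0 to 2.5 per placebo subject. The number of such subjects is not given, so no total can be computed.

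**The case against.** The strongest reply is that the protocol does in practice treat 6.8 as the home of the missed-dose rules. Section 6.7.5.3 classes doses withheld for an AE as missed doses under 6.8. The Day 2 text in 6.3.2.2 refers to 6.8 for delays, and 6.7.3.2 describes the GI hiatus as an exception to the rules there. This has force, but it is not a precedence clause. Section 7.11.2 is worded as an obligation and points to 4.3.1, not to 6.8. A site reading it has no signal that another instruction exists, so the 4-dose contradiction stands.

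On repeated lapses the reply is stronger. A reader might infer that the three sections give opposite instructions for repeated 3-day lapses generally. They do not: for non-compliance in Up-dosing all three stop the subject. On Maintenance, 4.3.1 and 7.11.2 are silent rather than permissive, and a site applying every section would stop under 6.8. What remains is a difference of scope.

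A reader might also infer that 7.11.2 stops children whose interruptions were ordered to treat an AE, because it attaches non-compliance explicitly only to the seven-day rule. The documents do not support that. The repeated-lapse clause continues the same sentence, 4.3.1 item 4 puts both limbs under non-adherence, item 5 handles medically indicated gaps separately, and 6.7.5.3 sends AE-withheld doses to 6.8, where the exemption is. The missing exemption is an editorial gap.

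**Conclusion.** Sections 6.8 and 7.11.2 contradict each other on the restart dose after exactly 4 consecutive missed doses in Up-dosing, and must be reconciled. The difference is at least one Table 2 level, or 17% to 50% of the current dose. This alone justifies the change, because it is a mandatory re-dosing instruction in the period that the protocol regards as highest risk for missed doses. No view is taken on which instruction is right.

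The Maintenance mismatch is secondary. It can turn a subject into a primary-endpoint failure under 9.2.1, but only a subject who would otherwise have responded changes the response rate. It would be tempting to conclude that the primary result depends on which section a site follows. The documents do not support that: they give no lapse frequency, the 4-dose conflict does not stop anyone, and no sample-size or power figure changes.

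The reading rests on the text of the three sections; Figure 5, which accompanies 6.8, was not available.

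**What to change.** Name one section as governing for missed doses. Replace the corresponding text in the other sections, including 7.11.2 and 4.3.1 item 4 as needed, with a cross-reference. The governing text should state once each:

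- the instruction after exactly 4 missed doses, including whether only consecutive days count and, if the dose is reduced, by how much;
- whether the repeated-lapse rule covers Up-dosing only or Maintenance as well;
- which interruptions are exempt from that rule.

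The sponsor's clinical team decides the content. Figure 5 should be checked against the result. The cost is a wording amendment and a note to sites, with the approvals that section 11.1 requires for any amendment (sponsor, DSMC, IRB/EC and submission to the authorities). It needs no new data, visits or analysis.

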6.7.3.2 Assessment of Chronic/Recurrent Symptoms

GI symptoms were the most common potentially allergic symptoms to occur on a subacute, chronic, and/or recurrent basis during Phase 2 clinical trials with AR101. Atopic dermatitis, seasonal allergies, or asthma are other potentially non-acute allergic reactions that could be brought on or exacerbated by OIT. The absence of a clear temporal relationship between dosing and the emergence of recurrent symptoms may help to distinguish these from acute dosing-related symptoms.

If symptoms arise that suggest a chronic/recurrent reaction to IP, the dose level should be reduced. As with acute symptoms, the level of the dose reduction should be guided by the severity of the symptoms. Symptomatic treatment is permitted ([Section 5.9](#)), but should be used as a supplement to dose reduction, not a substitute for it.

For chronic/recurrent GI symptoms, especially upper GI symptoms, investigators are advised to have a low threshold for instituting a dose reduction and/or for considering early discontinuation of affected subjects from the study, owing to the potential for EoE.

For subjects determined to be having dose-limiting chronic/recurrent GI symptoms up to and including the 20 mg/d dose level, it is advised that dosing of IP be suspended for 4 weeks and resumed at a dose level of 3 mg/day for a minimum of 4 weeks, with the first dose given in the CRC under medical supervision. If tolerated, up-dosing may resume, with caution, according to the usual schedule, as tolerated. (Note: the 4-week suspension of dosing in response to chronic/ recurrent GI symptoms occurring up to and including the 20 mg/d level is the only protocol-specified exception to the rules for missed OIT delineated in [Section 6.8](#).)

For subjects who develop dose-limiting chronic/recurrent GI symptoms at the 40 mg/d dose level or above, dose reduction and re-escalation is to proceed as described in [Section 6.3.3](#).

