- Return to the CRC for repeat dosing at the current dose level under direct observation to confirm whether or not the dose level is tolerated
- Return to the CRC for dosing of a previously tolerated dose level, either a 1- or 2-step reduction (per investigator judgment, based on severity of reaction) and follow the procedures described in [Section 6.7.5.2](#).
- Institute the 4-week hiatus from dosing, with resumption of dosing at the 3 mg/d dose level, as permitted for recurrent GI symptoms occurring at or before the 20 mg dose level, as described in [Section 6.7.3.2](#).
- Discontinuation of dosing

Any subject who discontinues up-dosing due to severe or repeated allergic reactions to IP should have his or her immune cell characterization blood draw and CBC ([Section 8](#)) at, or as nearly as possible to, the time of the last dose and no later than at their Early Discontinuation Visit.

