- If IP has been withheld for **8 to 14 consecutive days** as treatment for an AE or due to a IP dispensing error, dosing may be reinitiated at approximately 25% of the last tolerated dose (to the nearest feasible available whole dose that is $\leq 25\%$ of the last tolerated dose) if the lapse in dosing occurred during the Up-dosing Period. If the lapse in dosing occurred during the Maintenance Period, dosing may, at the investigator's discretion, be reinitiated at 50% of the last tolerated dose (to the nearest feasible available whole dose that is $\leq 50\%$ of the last tolerated dose). The reduced dose is to be administered under supervision in the CRC. If tolerated, dose escalation may resume with dose increases of 1 dose level occurring no more frequently than weekly and no less frequently than every 4 weeks until the subject has returned to the dose level at which the lapse in dosing occurred. If symptoms occur, the dosing guidelines for the Up-dosing Period apply.
- If IP has been withheld for **≥ 15 consecutive days** for any reason, at any point in the study (with the exception of a dosing hiatus instituted for chronic/recurrent GI AEs at or before the 20 mg dose level, as per [Section 6.7.3.2](#)), the subject will be asked to return to the CRC 14 to 16 days following their last dose of IP to undergo an Early Discontinuation Visit ([Section 6.4](#)).

No attempt should be made to make up for a missed dose if greater than 6 hours have elapsed since usual time of dosing.

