7.3.3.2 Gastrointestinal AEs Resulting in Prolonged Disruption of Dosing (Events of Interest)

Gastrointestinal AEs, typically chronic/recurrent GI AEs, that result in a prolonged disruption of dosing will be considered AEs of interest (AEIs) and will be assessed longitudinally according to the procedures described below. For the purpose of delineating these AEIs, prolonged disruption of dosing is defined as withholding IP for > 7 days. This will include 3 categories of subjects:

- Any subject whose dose is withheld for > 7 days due to GI AEs and resumes dosing at a reduced dose level ([Section 6.7](#))

- Any subject who develops chronic/recurrent GI AEs at or before reaching the 20 mg dose level and resumes dosing after a 30-day dosing hiatus ([Section 6.7.3.2](#));
- Any subject who permanently discontinues dosing due to GI AEs ([Section 4.3.1](#)).

Subjects who fall into any of these 3 categories will be asked to fill out the PEESS v2.0 questionnaire, with the assistance of a parent or guardian, as appropriate, while symptomatic, at the time of treatment discontinuation, and then every month for 6 months thereafter. During the 6-month safety follow-up, subjects may complete the PEESS v2.0 at home and send it to the clinic, or they may complete it at the clinic if monthly clinic visits are required.

It should be noted that the PEESS v2.0 was not designed to establish a diagnosis of EoE, and has not been validated for use in subjects with GI symptoms of other etiologies. Furthermore, the discriminant validity of the questionnaire has not been reported in either longitudinal natural history or interventional studies. For these reasons, the use of the PEESS v2.0 to monitor the clinical course of GI symptoms must be considered exploratory. Nevertheless, the PEESS v2.0 has shown good content and construct validity ([Franciosi et al, 2011](#); [Martin et al, 2015](#)) and so holds promise for being a valuable tool to follow the clinical course of EoE or an EoE-like immune-mediated GI syndrome. Thus, the PEESS v2.0, could reveal trends toward symptomatic improvement or worsening that might otherwise go undetected.

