9.2 Study Endpoint Assessment

9.2.1 Primary Endpoint

The primary endpoint is the proportion of subjects who achieve desensitization as determined by tolerating 1000 mg as a single dose (2043 mg cumulative) of peanut protein (ie, a top single challenge dose of 1000 mg) with no more than mild symptoms at the Exit DBPCFC (ie, responders).

An ITT analysis will be performed as the primary efficacy analysis to test for a treatment difference in the response rate. All individuals failing to achieve the success definition described above will be considered treatment failures, as will subjects who fail to achieve and maintain a 300 mg daily dose of IP (escalation failure non-responders). All individuals

who drop out of the study or discontinue OIT prior to undergoing the Exit DBPCFC will be considered treatment failures (ie, Missing = Failure).

Fisher's exact test will be used to test the treatment difference for desensitization and exact CIs will be constructed as follows: (1) exact Clopper Pearson confidence limits will be used for the binomial proportion and (2) exact unconditional confidence limits based on the score statistic will be used for the difference in proportions.

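### Protocol Section 7.11.2 stops any subject who misses 15 or more days, which catches the 4-week GI dosing hiatus that Sections 6.7.3.2 and 6.8 allow; Section 4.3.1 item 5 words that exception too broadly

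*Protocol*

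**What the plan says.** Protocol Section 7.11.2 (Individual Stopping Rules) states: "Missing 15 or more consecutive days of dosing for any reason also constitutes an individual stopping rule". No exception follows, and neither Section 6.7.3.2 nor Section 6.8 is cited. The only cross-reference is to Section 4.3.1, which it says "provides additional individual stopping rules".

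Five other places in the Protocol provide for a longer pause:

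- **Section 6.7.3.2** advises suspending IP for 4 weeks and restarting at 3 mg/day when dose-limiting chronic or recurrent GI symptoms appear at doses up to 20 mg/d. Its note says that this suspension for symptoms "occurring up to and including the 20 mg/d level is the only protocol-specified exception to the rules for missed OIT" set out in Section 6.8.
- **Section 6.8** has the same 15-day limit, also for any reason, but "with the exception of a dosing hiatus instituted for chronic/recurrent GI AEs at or before the 20 mg dose level".
- **Section 6.7.5.2** lists the pause among the investigator's options: "Institute the 4-week hiatus from dosing, with resumption of dosing at the 3 mg/d dose level".
- **Section 7.3.3.2** sets up PEESS v2.0 follow-up for, among others, a subject who develops chronic or recurrent GI AEs "at or before reaching the 20 mg dose level and resumes dosing after a 30-day dosing hiatus".
- **Section 4.3.1 item 5** terminates treatment after more than 14 consecutive days of medically indicated missed dosing, "except for the voluntary 30-day hiatus for AEs occurring at or before the 20-mg dose".

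**The concern.** There are two faults, of unequal weight.

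First, Section 7.11.2 has no carve-out for a pause that the Protocol itself advises. An investigator who follows Section 6.7.3.2 puts the subject into breach of a stopping rule roughly halfway through the pause.

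Second, Section 4.3.1 item 5 exempts a hiatus for AEs in general. Section 6.7.3.2 restricts it to chronic or recurrent GI symptoms and says that no other exception exists. Read literally, item 5 does not terminate a subject on a long non-GI pause whom Section 6.8 sends to Early Discontinuation.

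The statistical stake is outcome classification. Under Section 9.2.1, individuals "who drop out of the study or discontinue OIT prior to undergoing the Exit DBPCFC will be considered treatment failures". Two sites that read different sections could therefore give the same patient different primary outcomes for a reason unrelated to drug effect. The subject stopped under Section 7.11.2 would also lose a recovery route that the Protocol advises.

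**Working it through.** No sample-size, power or alpha figure is involved. The check compares sections and needs only simple arithmetic.

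**1. Does the hiatus meet the Section 7.11.2 threshold?**

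- Length in Sections 6.7.3.2 and 6.7.5.2: 4 weeks × 7 = 28 days.
- Length in Sections 4.3.1 item 5 and 7.3.3.2: 30 days.
- Threshold in Section 7.11.2: 15 consecutive days.
- Time still to run when the rule is met: 28 − 15 = 13 days, or 30 − 15 = 15 days.

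Either length crosses the threshold, so every subject who takes the hiatus in full is caught.

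**2. Could withheld doses fall outside the word 'missing'?** No. Section 6.7.5.3 treats doses withheld as part of AE treatment as a category of missed doses.

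**3. Does the reference to Section 4.3.1 import the exception?** No. Section 7.11.2 points there for further stopping rules. The exception in item 5 qualifies item 5's own limit of more than 14 days and nothing else.

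**4. Does the note in Section 6.7.3.2 override Section 7.11.2?** Not by its terms. It makes the hiatus an exception to the rules in Section 6.8 and does not mention Section 7.11.2.

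**5. Can Section 7.11.2 be read simply as a summary of Section 6.8?** Not safely, because the two differ on other missed-dose thresholds as well:

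| Situation | Section 7.11.2 | Section 6.8 |
|---|---|---|
| Non-compliance stop | 7 or more days | more than 7 days; 5 to 7 missed doses restart at about 50% |
| 4 missed days | restart at a reduced dose (rule is more than 3 days) | resume at the current dose, in clinic |
| 15 or more days, any reason | stop, no exception | stop, GI hiatus exempt |

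**6. Where in the schedule can it arise?** The dose levels below 300 mg in Table 2 are 3, 6, 12, 20, 40, 80, 120, 160, 200 and 240 mg, which makes 10. Four of them (3, 6, 12 and 20 mg) are at or below 20 mg. At 2 weeks each, that is 4 × 2 = 8 weeks of nominal up-dosing.

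**7. What does one wrongly stopped subject do to the primary endpoint?** Section 9.4 plans 120 AR101 and 40 placebo subjects. One subject moved from responder to failure lowers the response rate by 1/120 = 0.8 percentage points on AR101, or 1/40 = 2.5 points on placebo. These are upper limits per subject, since the subject might have failed anyway. The Protocol gives no count of subjects expected to take the hiatus, so no total can be calculated.

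**8. Item 5 for a non-GI pause of 15 or more days at or below 20 mg.** Item 5 read literally does not terminate. Section 6.8 does, the 14-day withholding limit in Section 6.7.5 does, and so does Section 7.11.2. The gap is confined to item 5.

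**The case against.** The best defence is that the intent is plain. The hiatus is stated or relied on in five sections, with its length, restart dose and exempt status given. It never happens by accident: an investigator must order it. To lose the subject, that same investigator would have to discontinue the subject on day 15 of a pause he or she had started, although a medical monitor is available for protocol questions. A reader who follows the reference to Section 4.3.1 also meets the exception there.

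On item 5, the definite article in "except for the voluntary 30-day hiatus for AEs occurring at or before the 20-mg dose" points to a hiatus defined elsewhere, and only one is defined. A non-GI subject is still stopped by three other rules.

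Any bias would probably be conservative. In ARC001 (Section 1.2.1), four AR101 subjects and no placebo subjects discontinued because of AEs, and two more AR101 subjects left for reasons that included GI AEs. On that pattern, wrongly stopped subjects would mostly be on AR101 and would lower its response rate.

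Much of this stands. It limits the likely number affected, makes a false efficacy claim from this source unlikely, and leaves the item 5 point with little practical effect. It does not correct Section 7.11.2. That section is an operative stopping rule, its text is unqualified, and it already departs from Section 6.8 on other thresholds, so a site or monitor cannot be sure which section governs.

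**Conclusion.** The point holds. Section 7.11.2 is wrong as written: applied literally, it discontinues every subject who completes the hiatus advised in Section 6.7.3.2 and exempted in Section 6.8, and Section 9.2.1 then scores that subject as a failure. Item 5 of Section 4.3.1 is probably shorthand for the same hiatus. Its missing GI limit is a lesser inconsistency, because other rules still stop a non-GI subject.

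The exposure is confined to the four dose levels up to 20 mg, nominally the first 8 weeks of up-dosing. The number of subjects is unknown and probably small. The consequence assumes that at least some sites apply Section 7.11.2 in preference to Sections 6.7.3.2 and 6.8, and the Protocol cannot show how often that would happen. This is a wording conflict that should be corrected. It does not undermine the design or the power of the trial.

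**What to change.** 1. **Section 7.11.2:** qualify the 15-day rule with the exception already used in Section 6.8, "with the exception of a dosing hiatus instituted for chronic/recurrent GI AEs at or before the 20 mg dose level", and cite Section 6.7.3.2.
2. **Section 4.3.1 item 5:** replace *AEs* with *chronic/recurrent GI AEs* and cite Section 6.7.3.2.
3. **Optional:** add the same cross-reference to the 14-day withholding limit in Section 6.7.5, which also has no exception, and use one hiatus length throughout in place of 4 weeks in some sections and 30 days in others.

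The cost is two short wording changes, plus the optional tidying. No procedures or patients are added.
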